6.6 Study Treatment Modifications

Treatment modifications (holds, delays, and reductions) for study treatment will be summarized in the P-Safety and Safety populations. Only modifications due to AE will be summarized by protocol-defined dose levels. Per protocol, cabozantinib and sorafenib doses can be reduced,

held, or discontinued, while atezolizumab infusions can be incomplete, interrupted, delayed, or discontinued but the dose cannot be reduced. Therefore, for the experimental arm, dose reduction summaries apply only to the cabozantinib treatment component. For summarization, atezolizumab delays will be considered dose holds and will also be counted as dose modifications. Incomplete or interrupted atezolizumab infusions will not be considered dose modifications and will be presented separately. Therefore, for the experimental arm (cabozantinib + atezolizumab), dose hold and dose modification summaries will be presented by individual treatment components as well as by combination.

The protocol allows only two levels of dose reduction for cabozantinib and sorafenib as shown below:

Table 7: Protocol Defined Dose Levels for Cabozantinib and Sorafenib

Study Arm Treatment	Dose Level Increase	Assigned Starting Dose	First Dose Level Reduction	Second Dose Level Reduction
Experimental arm cabozantinib	60 mg (qd)	40 mg (qd)	20 mg (qd)	20 mg (qod)
Single-agent arm cabozantinib	NA	60 mg (qd)	40 mg (qd)	20 mg (qd)
Control arm sorafenib	NA	800 mg (tdd)	400 mg (tdd)	400 mg (qod)

NA, not applicable; qd, once daily; qod, every other day; tdd, total daily dose.

A. The following summaries will be presented for Cabozantinib/Sorafenib:

i. For dose reductions due to AE

Categorical summaries for:

- Number of subjects with any dose reduction
- Number of subjects who received each dose level category
- Lowest non-zero dose level category received

Descriptive statistics for:

- Duration of treatment in months for each dose level category, defined for each subject as (cumulative number of days treatment was taken at each dose level) / 30.4375
- Time from first dose to first dose level reduction (days)
- Time from first dose to second dose level reduction (days)

ii. Summaries for dose holds due to AE:

- Descriptive statistics for number of dose holds (0 mg dose level) due to an AE per subject and classified as 1, 2, 3 and >3
- Descriptive statistics for total duration of dose holds per subject due to an AE and classified as ≥ 7 days, ≥ 14 days, and ≥ 21 days. Duration of each dose hold is calculated as (stop date of hold – start date of hold + 1)
- Frequency counts and percentages for subjects with duration of holds due to an AE classified as any number of days, ≥ 7 days, ≥ 14 days, and ≥ 21 days
- Descriptive statistics for duration of dose holds per dose hold and per subject due to an AE, calculated as (stop date of hold – start date of hold + 1)
- Descriptive statistics for time to first dose hold, time to first dose hold that was ≥ 7 days, ≥ 14 days, and ≥ 21 days. The time to dose hold is calculated as (start date of the hold – first dose date + 1)
- Descriptive statistics for time to second dose hold, time to second dose hold that was ≥ 7 days, ≥ 14 days, and ≥ 21 days

iii. Summaries for dose modifications (defined as a reduction or hold) due to AE:

- Frequency counts and percentages for subjects with any dose modifications
- Descriptive statistics for number of dose modifications (0-4)
- Descriptive statistics for time to the first dose modification
- Descriptive statistics for time to the second dose modification

The protocol allows (subject to Sponsor approval) escalation of cabozantinib dose from 40 mg qd to 60 mg qd for subjects in the experimental arm depending tolerance of the 40 mg dose level for at least 4 weeks. Summaries will be provided for number of subjects in the experimental arm who have their cabozantinib dose increased from 40 mg (qd) to 60 mg (qd). The duration on the 60 mg (qd) dose will also be summarized for these subjects. Note that any subsequent reduction from the sponsor-approved 60 mg (qd) dose level due to AE will be summarized separately as detailed earlier in this section with up to 3 levels of reductions.

B. The following summaries will be presented for Atezolizumab:

- Number of subjects with any incomplete infusion
- Number of subjects with any interrupted infusion
- Number of subjects with dose delay due to an AE (0, 1, 2, 3 and >3)
- Frequency counts and percentages for subjects with total duration of delay due to AE classified as any number of days, ≥ 7 days, ≥ 14 days, and ≥ 21 days
- Frequency counts and percentages for subjects with duration of delay due to an AE classified as any number of days, ≥ 7 days, ≥ 14 days, and ≥ 21 days
- Descriptive statistics for time to the first dose delay
- Descriptive statistics for time to the second dose delay

6.7 Study Treatment Non-Compliance and Dosing Errors

Treatment non-compliance and dosing errors for reasons other than AE will be summarized in the P-Safety and Safety populations. Frequency counts and percentages will be presented by treatment groups for:

- Subjects with dose hold (0 mg) due to non-compliance
- Subjects who received dose $>$ maximum allowed dose level at any time (60 mg qd for cabozantinib, even for subjects who started at 40 mg qd; 800 mg for sorafenib)
- Subjects who received non-protocol specified dose level (\leq maximum allowed dose level) at any time due to non-compliance
- Subjects who received non-protocol specified dose level (\leq maximum allowed dose level) at any time due to site/logistic error or other reason

6.8 Non-Protocol Anticancer Therapy (NPACT)

For the purpose of supporting safety evaluations:

Subsequent non-radiation NPACT will be summarized by ATC text and WHO Drug base substance preferred name in the P-Safety and Safety populations.

For the purpose of supporting efficacy evaluations:

Subsequent NPACT, including radiation therapy, will be summarized by treatment group in the PITT and ITT populations as follows:

- Based on the non-radiation therapy received subjects will be categorized into one or more of the following categories: systemic, local, or unknown and all NPACTs falling under these categories will be summarized by ATC text and WHO Drug based substance preferred name
- Time to first systemic NPACT will be summarized by descriptive statistics
- Frequency counts and percentages will be presented for radiation therapy indication, type, and site

6.9 Concomitant and Subsequent Surgeries/Procedures

Post-randomization radiation therapy and surgery/procedures that impacted the target lesion(s) (Yes, No, Unknown) will be summarized by treatment group for subjects in the PITT, ITT, P-Safety and Safety populations.

6.10 Concomitant Transfusions

Concomitant transfusions will be summarized by transfusion type and treatment group for subjects in the P-Safety and Safety populations.

7 EFFICACY ANALYSES

Efficacy summaries for primary, secondary, and additional endpoints will include only data collected in the Core period. No efficacy analyses will be conducted on data collected in the Crossover Phase.

7.1 Primary Efficacy Endpoints

The two primary efficacy endpoints for this study are duration of PFS per BIRC and duration of OS. Formal hypothesis tests are planned for these endpoints.

7.1.1 Duration of Progression-Free Survival (PFS)

7.1.1.1 Definitions and Conventions

Only adequate tumor assessments (ATAs) will be considered in the determination of radiographic progression and censoring dates. For the purpose of this study, an ATA is defined as one that results in a time point assignment of complete response, partial response, stable disease/(non-CR, non-PD), or progression.

The recorded date of radiographic progression is the date of the tumor assessment visit at which progression is declared. If multiple scan dates are associated with a tumor assessment visit, the earliest scan date within the set will be chosen as the progression date.

7.1.1.2 Primary Estimand

The primary estimand for PFS is the difference in survival functions between treatment conditions in the duration of radiographic progression-free survival in the targeted population:

- irrespective of whether the assigned study treatment was given
- irrespective of clinical deterioration
- irrespective of whether local radiation was given to bone
- irrespective of surgical resection of non-target lesions
- in absence of any surgery to resect tumor lesions
- in absence of any other systemic or local non-protocol anti-cancer treatment
- in absence of any local radiation to soft tissue
- in absence of missing pre-randomization tumor assessment
- in absence of two or more missing consecutive adequate tumor assessments

Derived as follows:

Estimand attribute ¹	Primary definition		Rationale (as needed)
Population	Subjects randomized into the study intended to include patients with advanced HCC who have not received previous systemic anticancer therapy.		The initial clause “Subjects randomized into the study intended to include...” is included to align the estimand with the application of the ITT principle expected by regulatory reviewers
Endpoint	Duration of radiographic progression-free survival		
Intercurrent events	Event	Strategy	Rationale (as needed)
	Receipt of non-assigned study treatment or non-receipt of study treatment	Treatment policy	This strategy applied to align the estimand with the application of the ITT principle expected by regulatory reviewers.
	Clinical deterioration	Treatment policy	This strategy applied due to the nature of the primary endpoint, which is radiographic PFS.
	Receipt of local radiation to bone	Treatment policy	This strategy applied as local radiation to bone is typically palliative and does not directly confound radiographic evaluations of soft tissue.
	Surgical resection of non-target tumor lesions	Treatment policy	This strategy applied as target lesions are the primary focus of RECIST 1.1 evaluations.
	Surgical resection of target tumor lesions	Hypothetical	This strategy arises as a consequence of the convention of censoring for these intercurrent events that confound radiographic tumor assessments per RECIST 1.1., and the assumption in the Kaplan-Meier model that censored subjects would have behaved in a fashion similar to those not censored, i.e. not experienced these intercurrent event(s)
	Receipt of systemic non-protocol anti-cancer medications	Hypothetical	
	Receipt of local non-protocol anti-cancer medications	Hypothetical	
	Receipt of local radiation to soft tissue for disease under study	Hypothetical	
	Missing pre-randomization tumor assessment	Hypothetical	
Population summary	Difference in survival functions between treatment conditions.		

¹See Appendix E for estimand terminology

¹See Appendix E for estimand terminology

7.1.1.4 Primary Definition

For the primary analysis directed toward the primary estimand, duration of PFS is defined as the time from randomization to the earlier of either the date of radiographic progression per BIRC or the date of death due to any cause.

PFS (months) = (earliest date of progression, death, censoring – date of randomization + 1)/30.4375

General censoring rules for the primary analysis of PFS are described below, with details provided in Table 7Table 8 (analysis ID PFS-EP-1):

- Subjects who receive systemic or local NPACT or non-protocol radiation therapy (other than to bone) or surgery to resect target lesions before experiencing an event will be right censored at the date of the last tumor assessment prior to the date of initiation of subsequent therapy/surgery. If there is no such tumor assessment post randomization, the subject will be right censored on the date of randomization.
- Subjects who have not experienced an event (and are not otherwise censored) at the time of data cutoff will be right censored on the date of their last tumor assessment post randomization that is on or prior to the data cutoff date. If there is no such tumor assessment post randomization, the subject will be right censored on the date of randomization.
- Subjects who miss 2 or more scheduled tumor assessments followed by an event will be right censored on the date of their most-recent tumor assessment prior to the missing assessments. If there is no such tumor assessment post randomization, the subject will be right censored on the date of randomization.

7.1.1.5 Hypothesis

The hypotheses to be evaluated in the analysis of the PFS are:

$$H_0: S(t)_{\text{cabozantinib+atezolizumab}} = S(t)_{\text{sorafenib}}$$

$$H_A: S(t)_{\text{cabozantinib+atezolizumab}} \neq S(t)_{\text{sorafenib}}$$

where $S(t)_{\text{cabozantinib+atezolizumab}}$ and $S(t)_{\text{sorafenib}}$ are the survivor functions for PFS for the experimental and control arms, respectively.

7.1.1.6 Primary Analysis

The timing of this analysis is event-driven, and it will be conducted after at least 257 events have been observed in the PITT population. It is designed to include progression events as determined by the BIRC per RECIST 1.1. Clinical deterioration determined by the investigator will not be considered progression events. The actual number of events at the time of analysis may be higher than 257 due to the logistics of estimating event counts in an ongoing multicenter clinical study and predicting cutoff dates for analysis.

The hypothesis testing between experimental arm (cabozantinib + atezolizumab) compared to the control arm (sorafenib) will be performed using the stratified log-rank test with a 2-sided $\alpha=0.01$ level of significance. The stratification factors are as described in Section 2.4 and the values used for analysis will be those recorded in the IRT.

The median duration of PFS along with the associated 99% and 95% confidence intervals (CI) for each study treatment arm will be estimated using the Kaplan-Meier method. The stratified hazard ratio (HR) and its 99% and 95% CI will be estimated using a Cox proportional-hazard model with treatment group as the independent variable using the same stratification factors as were used for the log-rank test.

If the p-value for the stratified log-rank test is less than the critical value for rejecting the null hypothesis and the HR ($\lambda_{\text{cabozantinib + atezolizumab}} / \lambda_{\text{sorafenib}}$) is < 1 , the null hypothesis of no difference between the two study treatment arms will be rejected and it will be inferred that duration of PFS is greater in the experimental arm (cabozantinib + atezolizumab) compared to the control arm (sorafenib).

The unstratified versions of all the above analyses will also be conducted.

7.1.1.7 Sensitivity and Supplemental Analyses

Event and censoring definitions for the primary analysis (PFS-EP-1) and 3 sensitivity analyses (PFS-EP-2, PFS-EP-3, PFS-EP-4) directed at the primary estimated for PFS are provided in Table 8.

The three sensitivity analyses evaluate the impact of different assumptions or conditions that potentially influence the estimate of the primary estimand:

- The PFS-EP-2 definition evaluates the influence of potentially inconsistent tumor assessment intervals between arms. For subjects who experience radiographic

progression, it assigns the date of the scheduled visit as the event date, rather than the date of recorded progression.

- The PFS-EP-3 definition evaluates the influence of the assessor of radiographic progression and is based on RECIST 1.1 evaluations by the investigator rather than the BIRC.
- The PFS-EP-4 definition evaluates the influence of the missing tumor assessments. It classifies subjects who experience ≥ 2 consecutive missing scheduled ATA immediately prior to documented radiographic progression as having an event, rather than being censored, at the date of the last ATA prior to the missing visits.

Event and censoring definitions for 3 supplemental analyses (PFS-EA1-1, PFS-EA2-1, PFS-EA2-1) directed at the two alternative estimands for PFS are provided in Table 9.

- The PFS-EA1-1 definition is the primary analysis of alternative estimand 1.
- The PFS-EA2-1 definition is the primary analysis of alternative estimand 2.
- The PFS-EA2-2 definition is a sensitivity analysis of alternative estimand 2, similar to PFS-EP-4 (defined above).

Four additional “differential” sensitivity analyses (PFS-EP-11, PFS-EP-12, PFS-EP-13, PFS-EP-14) directed at the primary estimand will be conducted to evaluate the impact of potentially informative censoring. These analyses are based on the primary analysis PFS-EP-1 but with selected censored subjects re-classified as events, differentially by treatment arm, as shown in Table 10. These are highly conservative definitions intended to evaluate potential bias. The directions of treatment effects are of key interest rather than the values of inferential statistics.

The concordance in assessment of radiographic progression and the date between BIRC and investigator will be summarized.

All sensitivity and supplemental analyses will include all subjects in the PITT population. Tabulated summaries of survival times, hazard ratios, and log rank test statistics as well as graphs of survival functions will be presented.

Table 8: Event and Censoring Rules for Primary and Sensitivity Analyses of Primary PFS Estimand

Estimand	Primary		Primary		Primary		Primary	
Analysis type	Primary		Sensitivity		Sensitivity		Sensitivity	
Analysis purpose	Primary		Evaluate assessment time bias		Evaluate assessor bias		Evaluate potentially informative censoring	
Analysis ID	PFS-EP-1		PFS-EP-2		PFS-EP-3		PFS-EP-4	
Analysis name	rPFS per BIRC		Uniform dates		rPFS per Investigator		rPFS per BIRC despite missing ATA	
Estimand endpoint	Radiographic PD		Radiographic PD		Radiographic PD		Radiographic PD	
Population	PITT		PITT		PITT		PITT	
Situation	Outcome	Date of Outcome	Outcome	Date of Outcome	Outcome	Date of Outcome	Outcome	Date of Outcome
Radiographic PD per RECIST 1.1 per BIRC	event	date of recorded PD	event	date of scheduled visit (or next scheduled visit if between visits)	NA	NA	event	date of recorded PD
Radiographic PD per RECIST 1.1 per Investigator	NA	NA	NA	NA	event	date of recorded PD	NA	NA
Death	event	date of death	event	date of death	event	date of death	event	date of death
Intercurrent events (excluding those with Treatment Policy strategy for all estimands)								
Clinical deterioration	NA	NA	NA	NA	NA	NA	NA	NA
Systemic NPACT (medications)	censored	date of last ATA* before first initiation of therapy	censored	date of last ATA* before first initiation of therapy	censored	date of last ATA* before first initiation of therapy	censored	date of last ATA* before first initiation of therapy
Local NPACT (medications)	censored	date of last ATA* before first initiation of therapy	censored	date of last ATA* before first initiation of therapy	censored	date of last ATA* before first initiation of therapy	censored	date of last ATA* before first initiation of therapy
Surgical resection of target tumor lesion(s)	censored	date of last ATA* before target lesion resection	censored	date of last ATA* before target lesion resection	censored	date of last ATA* before target lesion resection	censored	date of last ATA* before target lesion resection
Local radiation: to soft tissue for disease under study	censored	date of last ATA* before non-target lesion resection	censored	date of last ATA* before non-target lesion resection	censored	date of last ATA* before non-target lesion resection	censored	date of last ATA* before non-target lesion resection
Missing data								
No baseline ATA	censored	date of rand.	censored	date of rand.	censored	date of rand.	censored	date of rand.
≥ 2 consecutive missing scheduled ATA immediately prior to analysis event	censored	date of last ATA* before missing visits	censored	date of last ATA* before missing visits	censored	date of last ATA* before missing visits	event	date of last ATA* before missing visits
Observation ongoing								
None of the above	censored	date of last ATA*	censored	date of last ATA*	censored	date of last ATA*	censored	date of last ATA*

ATA, adequate tumor assessment; BIRC, blinded independent review committee; ITT, intent-to-treat; NA, not applicable; PD, progressive disease; NPACT, non-protocol anti-cancer therapy (medications including radiopharmaceuticals but excluding local radiation)

Date of recorded PD = see SAP text.

* or date of randomization if no post-randomization ATA

Blue cells indicate changes from primary analysis.

Table 9: Event and Censoring Rules for Supplementary Analyses of Alternative PFS Estimands

Estimand	Alternative 1		Alternative 2		Alternative 2	
Analysis type	Supplementary		Supplementary		Supplementary	
Analysis purpose	Alternate progression definition		Alternate progression definition		Evaluate potentially informative censoring	
Analysis ID	PFS-EA1-1		PFS-EA2-1		PFS-EA2-2	
Analysis name	Investigator claims		rPFS or sNPACT		rPFS or sNPACT despite missing ATA	
Estimand endpoint	Radiographic or clinical PD		Radiographic PD or initiation of systemic NPACT		Radiographic PD or initiation of systemic NPACT	
Population	PITT		PITT		PITT	
Situation	Outcome	Date of Outcome	Outcome	Date of Outcome	Outcome	Date of Outcome
Radiographic PD per RECIST 1.1 per BIRC	NA	NA	event	date of recorded PD	event	date of recorded PD
Radiographic PD per RECIST 1.1 per Investigator	event	date of recorded PD	NA	NA	NA	NA
Death	event	date of death	event	date of death	event	date of death
Intercurrent events (excluding those with Treatment Policy strategy for all estimands)						
Clinical deterioration	event	date of determination of clinical deterioration	NA	NA	NA	NA
Systemic NPACT (medications)	event	date of first initiation of therapy	event	date of first initiation of therapy	event	date of first initiation of therapy
Local NPACT (medications)	event	date of first initiation of therapy	censored	date of last ATA* before first initiation of therapy	censored	date of last ATA* before first initiation of therapy
Surgical resection of target tumor lesion(s)	event	date of last ATA* before target lesion resection	censored	date of last ATA* before target lesion resection	censored	date of last ATA* before target lesion resection
Local radiation: to soft tissue for disease under study	event	date of last ATA* before non-target lesion resection	censored	date of last ATA* before non-target lesion resection	censored	date of last ATA* before non-target lesion resection
Missing data						
No baseline ATA	censored	date of rand.	censored	date of rand.	censored	date of rand.
≥ 2 consecutive missing scheduled ATA immediately prior to analysis event	censored	date of last ATA* before missing visits	censored	date of last ATA* before missing visits	event	date of last ATA* before missing visits
Observation ongoing						
None of the above	censored	date of last ATA*	censored	date of last ATA*	censored	date of last ATA*

ATA, adequate tumor assessment; BIRC, blinded independent review committee; ITT, intent-to-treat; NA, not applicable; PD, progressive disease; NPACT, non-protocol anti-cancer therapy (medications including radiopharmaceuticals but excluding local radiation)

Date of recorded PD = see SAP text.

* or date of randomization if no post-randomization ATA

Blue cells indicate changes from primary analysis.

Table 10: Definitions for Differential Sensitivity Analyses of PFS to Further Evaluate Potentially Informative Censoring (based on PFS-EP-1)

Estimand	Primary							
Analysis type	Sensitivity							
Analysis purpose	Differential analyses to explore potentially informative censoring							
Analysis strategy	Selected censored subjects in primary analysis reclassified as events, differentially by assigned treatment arm, as shown below (green cells)							
Analysis ID	PFS-EP-11		PFS-EP-12		PFS-EP-13		PFS-EP-14	
Censoring category for subjects censored in PFS-EP-1 in PITT Population	Exp	Cntrl	Exp	Cntrl	Exp	Cntrl	Exp	Cntrl
rPD per INV but not BIRC	At recorded date of first rPD per INV		At recorded date of first rPD per INV		At recorded date of first rPD per INV	At recorded date of first rPD per INV	At recorded date of first rPD per INV	
Discontinued radiographic assessment for reasons other than rPD and no sNPACT	At date of last ATA		At date of last ATA		At date of last ATA		At date of last ATA	
sNPACT prior to rPD per INV or BIRC			At date of first sNPACT	At date of first sNPACT			At date of first sNPACT	

ATA, adequate tumor assessment; BIRC, blinded independent review committee; Cntrl, control arm; Exp, experimental arm; rPD, radiographic progressive disease per RECIST 1.1;

INV, investigator; sNPACT, systemic non-protocol anti-cancer therapy (medications including radiopharmaceuticals)

* or date of randomization if no post-randomization ATA

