9.2.2. Primary Analysis

9.2.2.1. Progression-Free Survival

The primary analysis of PFS is event-driven and will be conducted after at least 257 events have been observed in the PITT population (see [Section 9.1.1.1](#)). It is designed to include progression events as determined by the BIRC per RECIST 1.1. Clinical deterioration determined by the investigator will not be considered progression events.

General censoring rules for the primary analysis of PFS are described below:

- Subjects who receive systemic NPACT or nonprotocol radiation therapy (other than to bone) or surgery to resect target lesions before experiencing an event will be right censored at the date of the last tumor assessment prior to the date of initiation of subsequent therapy/surgery. If there is no such tumor assessment post randomization, the subject will be right censored on the date of randomization.
- Subjects who have not experienced an event (and are not otherwise censored) at the time of data cutoff will be right censored on the date of their last tumor assessment post randomization that is on or prior to the data cutoff. If there is no such tumor assessment post randomization, the subject will be right censored on the date of randomization.
- Subjects who miss 2 or more scheduled tumor assessments followed by an event will be right censored on the date of their most-recent tumor assessment prior to the missing assessments. If there is no such tumor assessment post randomization, the subject will be right censored on the date of randomization.

Hypothesis testing between the two treatment arms will be performed using the stratified log-rank test with a 2-sided 0.01 level of significance. The stratification factors will be the same as those used to stratify the randomization (see [Section 3.3](#)).

The median duration of PFS and the associated 95% and 99% CIs for each treatment arm will be estimated using the Kaplan-Meier method. The HR with 95% and 99% CIs will be estimated using a Cox regression model and will include the same stratification factors described above.

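### SAP Tables 8 and 9 date soft-tissue radiation from non-target lesion resection, contrary to SAP 7.1.1.4 and protocol 9.2.2.1; the rule can be recovered, but the cited table for primary PFS needs correcting

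*SAP*

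**What the plan says.** SAP 7.1.1.4 sets the general rule for primary PFS. It covers "Subjects who receive systemic or local NPACT or non-protocol radiation therapy (other than to bone", together with surgery on target lesions. Such subjects are "right censored at the date of the last tumor assessment prior to the date of initiation of subsequent therapy/surgery". The section passes the detail to a table: "with details provided in Table 7Table 8 (analysis ID PFS-EP-1". The doubled reference is a leftover, since Table 7 holds dose levels and Table 8 holds the event and censoring rules.

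In Table 8 (SAP 7.1.1.7) the row for soft-tissue radiation has the outcome censored and the date "date of last ATA* before non-target lesion resection" in all four columns, PFS-EP-1 to PFS-EP-4. Table 9 gives the same date in its three columns. There radiation is an event in PFS-EA1-1 and a censoring reason in PFS-EA2-1 and PFS-EA2-2.

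The primary estimand (SAP 7.1.1.2) handles resection of non-target lesions by treatment policy, with the reason "This strategy applied as target lesions are the primary focus of RECIST 1.1 evaluations". Soft-tissue radiation is handled as hypothetical. One bullet above the estimand table reads "in absence of any surgery to resect tumor lesions", without limiting this to target lesions.

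Protocol 9.2.2.1 has the same date rule as SAP 7.1.1.4, but its list is "Subjects who receive systemic NPACT or nonprotocol radiation therapy (other than to bone) or surgery to resect target lesions". Local non-protocol anticancer therapy (NPACT) is not in it. The SAP adds local NPACT in 7.1.1.4, in Table 8 and in the estimand bullet "in absence of any other systemic or local non-protocol anti-cancer treatment".

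The SAP addendum deals only with analyses that have more information or more events than planned. It does not touch these tables.

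**The concern.** Table 8 is the place the SAP names for the operative detail of PFS-EP-1, which is tested at 2-sided 1%. Its radiation row conflicts with the text that cites it, and it uses an event the estimand says is irrelevant. Someone programming from the table alone would meet a cell that cannot be applied to most irradiated subjects, or that dates them from the wrong procedure.

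The same columns supply dates for time to progression and duration of response (SAP 7.5.3 and 7.5.4), both exploratory. Best overall response is also cut off at the primary PFS censoring events (SAP 7.5.1).

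The second issue is that the two supplied documents list different reasons for censoring. For a subject who receives local drug therapy before progression by the blinded review, the SAP censors. On the protocol list, a later progression or death could count as an event.

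**Working it through.** **The plan's own figure.** Inputs (protocol 9.7, SAP 2.3): 257 events, HR 0.6, 2:1 allocation, 2-sided alpha 0.01, power 90%. The Schoenfeld formula gives:

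- Power: sqrt(257 × 2/9) × |ln 0.6| − 2.5758 = 7.557 × 0.5108 − 2.5758 = 1.2846, which is 90.05%.
- Smallest significant HR: exp(−2.5758 / 7.557) = 0.711, against 0.71 stated.

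The design reproduces. The event target is fixed, so nominal power is the same whichever wording is used. The point is about specification, not power.

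**Anchors in Table 8, column PFS-EP-1.**

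| Intercurrent event | Date counted back from | Own trigger? |
|---|---|---|
| Systemic NPACT | first start of that therapy | yes |
| Local NPACT | first start of that therapy | yes |
| Resection of target lesion | that resection | yes |
| Soft-tissue radiation | resection of a non-target lesion | no |

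The radiation row is the only therapy or surgery row dated from something other than its own trigger.

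**Can another row supply the date?** No. The table footnote defines NPACT as drugs, counting radiopharmaceuticals, and leaves local radiation out.

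**The literal result, compared with SAP 7.1.1.4.**

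| Irradiated subject | Table 8 as written | SAP 7.1.1.4 and protocol 9.2.2.1 |
|---|---|---|
| No non-target resection | no date defined | last assessment before radiation starts |
| Non-target resection at another time | last adequate assessment before that resection | last assessment before radiation starts |

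**Extent.** 4 cells in Table 8 + 3 in Table 9 = 7. In six of them the date is a censoring date. In one (PFS-EA1-1) it is an event date, for which SAP 7.1.1.4 and protocol 9.2.2.1 set no rule. Elsewhere in that column the NPACT rows date the event at first start of therapy, and the target-resection row dates it at the last assessment before surgery.

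**Local NPACT across the same seven analyses.** Censored in 4 + 2 = 6, an event in 1 (PFS-EA1-1), left uncensored in 0. No tabulated analysis therefore shows PFS by blinded review under the list in the supplied protocol.

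**What cannot be computed.** The documents do not say how many subjects had soft-tissue radiation, non-target resection or local NPACT before an event. With at least 257 events among 372 subjects, at most 372 − 257 = 115 are censored, but that ceiling covers every reason for censoring and does not estimate this one.

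**The case against.** The strongest reply is that the slip corrects itself. The row label names radiation. The Table 8 subheading for intercurrent events leaves out those handled by treatment policy in every estimand, and non-target resection is handled that way in the primary and both alternative estimands. SAP 7.1.1.4 and protocol 9.2.2.1 agree on the date. A careful programmer would see an unusable cell and go back to the text. This stands, and it limits the point to a correction. It does not remove the need for one, because the table is the detail the SAP cites for an alpha-bearing test.

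Three stronger readings are tempting, and the documents do not support them:

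- A reader might infer that the SAP's estimand contradicts itself on surgery. Two bullets before the loose one, and again in the estimand table, non-target resection is expressly set aside. The bullet is badly worded, but the rule is not in doubt.
- A reader might infer that local-NPACT censoring is an undocumented change from the protocol. The SAP states that it is based on Amendment 2.0, whereas the supplied protocol describes Amendment 3.0, so the wording the SAP was written against cannot be checked. The protocol calls its list general and leaves analysis details to the SAP, and the SAP states its own rule openly. Protocol 7.2 also discourages local treatment until radiographic progression is established, and investigator reads drive treatment. The difference therefore matters mainly where local therapy follows investigator progression that the blinded review has not yet called. PFS-EP-3 and Table 10 partly examine that situation.
- A reader might infer that the scope of NPACT is generally confused. SAP 6.8 does count radiation as NPACT, but it describes summary tables, not censoring. What remains is narrow: non-drug local procedures such as ablation have no row in Table 8.

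**Conclusion.** The radiation row is wrong as written in all seven cells of Tables 8 and 9, including primary PFS-EP-1, and the addendum does not correct it. The intended censoring date is recoverable from SAP 7.1.1.4 and protocol 9.2.2.1, so a reader should not infer that primary PFS is biased or its test invalid. Neither the number of subjects affected nor a direction can be derived from the documents, and nominal power is unchanged.

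The local-NPACT difference is real between the two supplied texts and calls for reconciliation, nothing stronger. The bullet on surgery and the missing row for non-drug procedures are minor wording matters.

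The conclusion rests on the table text as extracted. The same phrase recurs in every column, so displacement of a single cell is an unlikely explanation. It is worth correcting before the data are analyzed, because the correction is small and the table governs a formal test.

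**What to change.** By SAP addendum:

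1. Table 8, all four columns, and Table 9, PFS-EA2-1 and PFS-EA2-2: set the date for the radiation row to the last adequate tumor assessment before the first start of soft-tissue radiation, keeping the footnote that falls back to randomization.
2. Table 9, PFS-EA1-1, where radiation is an event: set the date to the first start of soft-tissue radiation, matching the NPACT rows in that column.
3. SAP 7.1.1.2: limit the surgery bullet to target tumor lesions.
4. Add one line saying how non-drug local procedures such as ablation are handled, and remove the stray Table 7 reference in 7.1.1.4.

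Separately, reconcile the censoring lists in protocol 9.2.2.1 and SAP 7.1.1.4 on local NPACT and record the outcome under SAP 4.9. If this changes the primary rule in substance, SAP 4.9 calls for a revised plan instead of an addendum. A supportive analysis by blinded review under the protocol list would be informative but is optional.

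The cost is seven cells and a few sentences, with no new data and no change to sample size or alpha. The documents do not show whether the database has been locked. The correction should be approved before lock if that is still possible.
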